### 3. METHODOLOGY

#### 3.1. Design overview

This study involves a single-blind, continuous recruitment short exposure, stepped-wedge cluster randomized controlled trial (SWT). Participants will be recruited from one of 6 sites in Ontario. Collectively, these 6 sites have approximately 710 admissions to out-patient stroke rehabilitation annually (St. John's – Sunnybrook: 150; Toronto Rehab – University Centre: 160; Toronto Rehab – Rumsey: 130; West Park: 150; St. Joseph's Care Group: 60; Hamilton Health Sciences: 60). At a randomly-determined time within the study period (see Figure 1), each site will transition from the control intervention (group aerobic exercise only; GAE) to the experimental intervention (PROPEL). New participants will be recruited continuously throughout the study period and will either complete the GAE or PROPEL intervention, depending on which program that site is administering at the time at which they are admitted to rehabilitation.

Each site will be staffed by a research assistant (RA) and a physiotherapist (PT). The RA will be responsible for recruiting participants and collecting data. The PT will administer the interventions.

	2017							2018							
	G1	G2	G3	G4	G5	G6	G7	G8	G9	G10	G11	G12	G13	G14	G15
Site A	1	1	1	1	1	1	1	1	1	1	1	1	1	1	1
Site B	0	0	0	1	1	1	1	1	1	1	1	1	1	1	1
Site C	0	0	0	0	0	0	1	1	1	1	1	1	1	1	1
Site D	0	0	0	0	0	0	0	0	0	1	1	1	1	1	1
Site E	0	0	0	0	0	0	0	0	0	0	0	0	1	1	1
Site F	0	0	0	0	0	0	0	0	0	0	0	0	0	0	0

**Figure 1: Intervention allocation schedule.** G1, G2 etc. are the 6-week long group aerobic exercise (GAE) or PROPEL groups. Each site should be able to complete 8 groups per year; however, only 7 groups will be completed in 2017 to allow for additional time at the start of the year to obtain research ethics approval, inter-institutional agreements, and pilot implementation at all sites (see also Figure 3). '0' indicates that the site will complete GAE in that time period, whereas '1' indicates that they will complete PROPEL. A simple randomization procedure will be used to determine the time at which each site transitions from GAE to PROPEL. Sites will be allocated in order by drawing names from a hat; e.g., the 1st site to be drawn will be Site A, the 2nd will be Site B, etc.

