#### 3.2. Rationale for SWT design

The group format is essential to PROPEL (see below). We experienced from our pilot study that there was often a delay to start the group until there were  $\geq 3$  people referred. Therefore, a study design whereby individual participants are randomly allocated to either GAE or PROPEL would be problematic as there would be even greater delays in starting the groups. Likewise, a traditional cluster randomized controlled trial, where sites are randomly assigned to either complete GAE or PROPEL, would not be ideal due to the relatively low number of sites (6), and thus, reduced statistical power. Therefore, the SWT is a pragmatic trial design that is suitable for evaluating interventions that are implemented routinely at the level of cluster. It balances the need for robust evaluation with logistic constraints in program evaluation, particularly in cases of inter-site variability. Indeed, previous authors have argued that well-designed and executed SWTs can be as rigorous as traditional cluster randomized trials.

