### 3.8. Statistical analysis

We will compare cohort descriptors between the two phases (GAE and PROPEL) using t-tests, Mann-Whitney *U* tests, or chi-square tests, as appropriate. If phases significantly differ at baseline on cohort descriptors these measures may be used as covariates in the analysis. To test our primary hypothesis, we will compare the proportion of active and inactive individuals at the final assessment point (6 months post-intervention) using mixed-model logistic regression, with fixed effects of time and phase and random effect of cluster (site). We will also examine between-phase differences in physical activity at the 1-month and 4-month time points, which could reveal short-term benefits of PROPEL, even if there are no differences at 6-months. A similar mixed-model ANOVA will be used to compare SSEE, SOEE, and BBAQ scores between programs to test the secondary hypothesis.

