### 3.9. Sample size

We expect that approximately 25% of people who complete GAE and 50% of individuals who complete PROPEL will be classified as 'active'. A sample of 96 per phase will provide 80% power to detect a 25% to 50% difference at alpha of 0.05 for the 6 sites taking into account an intracluster correlation of 0.05. The sample size calculation was run using PASS Version 12 (Hintze, J, 2014, NCSS, LLC. Kaysville, Utah). We will aim to recruit 120 participants total per phase to account for a conservative 20% drop-out rate; note that in our previous studies where participants were recruited at discharge from rehabilitation and followed for up to 6 months, the rate of withdrawal was much lower (<12%). There are 710 admissions annually to out-patient stroke rehabilitation at all sites combined. We conservatively estimate that approximately 40% of these individuals will be eligible for the study and, of these, 50% will consent to participate. Thus, we expect to recruit ~140 participants annually to meet the target sample size with ~2 years of recruiting (see timelines and milestones: Figure 3). Target sample sizes for each site are: St John's – 60, West Park – 60, Toronto Rehabilitation Institute (both sites) – 116, St Joseph's Care Group – 24, Hamilton Health Sciences – 24.

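### The primary phase test rests on 6 sites and names no small-sample or randomisation-based inference; with the ordinary Wald or likelihood-ratio reference, type I error is about 7–9% at the planning ICC of 0.05, against a stated 5%

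*Combined protocol and SAP*

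**What the plan says.** Section 3.8 (Statistical analysis) defines the primary comparison: "we will compare the proportion of active and inactive individuals at the final assessment point (6 months post-intervention". The model is "mixed-model logistic regression, with fixed effects of time and phase and random effect of cluster (site". A published review of stepped-wedge analyses is cited in support. No section names the test of the phase effect, its reference distribution, degrees of freedom, interval method or analysis software.

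Section 3.2 (Rationale for SWT design) does recognise that there are few sites. It argues that a parallel cluster trial would not be ideal "due to the relatively low number of sites (6), and thus, reduced statistical power". Power is the only consequence it draws.

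Section 3.9 (Sample size) claims 80% power "at alpha of 0.05 for the 6 sites taking into account an intracluster correlation of 0.05". It does not discuss whether that alpha is held with six clusters.

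The Figure 1 legend in section 3.1 describes the randomisation: "Sites will be allocated in order by drawing names from a hat".

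**The concern.** With six sites, the between-site variance is estimated from six units. Ordinary mixed-model output refers the phase estimate to a normal or chi-square distribution, which makes no allowance for how poorly that variance is known. When the estimate falls on zero, the model reduces to logistic regression on independent participants. The standard error is then too small if sites really do differ.

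Two things are at stake. The primary test may reject a true null more often than the 5% stated in section 3.9, with an interval that is too narrow. And because the reference is left open, it could be chosen after the data are seen. The same fitted model gives a test with size well above or well below 5%, depending on that choice.

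**Working it through.** **1. The plan's own figure.** For 25% v 50%, two-sided alpha 0.05 and 80% power, the unpooled formula gives (1.960 + 0.842)² × (0.1875 + 0.25) / 0.25² = 54.94 per phase. The design effect with 96/6 = 16 per site is 1 + 15 × 0.05 = 1.75. Then 54.94 × 1.75 = 96.1, and 96/0.8 = 120. Section 3.9 is reproduced, as a parallel-cluster calculation with a normal reference. It contains no small-sample allowance.

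**2. Inputs to the null simulation.**
- Schedule (Figure 1): 6 sequences × 15 groups; sites switch at G1, G4, G7, G10, G13 or never; 15 + 12 + 9 + 6 + 3 + 0 = 45 of 90 site-periods are PROPEL.
- Site sizes: in proportion to the section 3.9 targets, 60 + 60 + 116 + 24 + 24 = 284. The 116 covers two sites. It was split 64/52 by their admissions of 160 and 130 in the main set, and 58/58 in the repeat (both assumptions).
- Evaluable N: 2 × 96 = 192, or 0.8 × 284 = 227.
- Site SD on the logit scale for latent ICC 0.05: √[(0.05/0.95) × π²/3] = 0.416. For ICC 0.05 on the proportion scale at 37.5% active: √[0.05/(0.375 × 0.625)] = 0.46.
- Common rate under the null: 25% or 37.5%.
- Time: calendar time, coded as linear, five 3-group steps or 15 categories, because section 3.8 does not give the coding.
- Fit: maximum likelihood with Gauss-Hermite quadrature.

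**3. Type I error (nominal 5%).**

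| Setting | Wald z | Likelihood ratio |
|---|---|---|
| ICC 0.05, N 192, 25% | 7.9% | 7.1% |
| ICC 0.05, N 227, 25% | 8.3% | 7.5% |
| ICC 0.05, N 192, 37.5% (two runs) | 8.5%, 9.4% | 7.5%, 7.8% |
| ICC 0.05, N 227, 37.5% | 8.8% | 7.5% |
| ICC 0.05, separately coded repeat | 7.6–8.7% | 6.8–7.7% |
| ICC 0.01 | 5.3–6.5% | 5.3–6.1% |
| ICC 0 | 4.9% | 4.8% |
| ICC 0, separately coded repeat | 4.4–5.4% | 4.2–5.2% |

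The named ICC 0.05 rows use five-step time and 8,000 replicates (6,000 for the second of the two runs), with a Monte Carlo SE of about 0.3 points. The repeat used 4,000–8,000 replicates. In the main set, linear time gave 7.8/7.3% and 15 time categories 8.3/7.5% to 9.0/8.0%. Smaller repeats (1,500–4,000 replicates) scattered more widely at ICC 0.05, at 7.1–9.7% for Wald and 5.7–8.1% for likelihood ratio. About 7–9% is a fair summary.

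**4. Mechanism.** At ICC 0.05 the site variance was estimated as essentially zero in 25–44% of null trials. In one run (N 192, 25%), 44% of fits were at zero and rejected 11.5% of the time; the rest rejected 4.8%. This gives 0.44 × 11.5 + 0.56 × 4.8 = 7.7%, against 7.8% observed. In another (N 227, 37.5%), 0.28 × 16.8 + 0.72 × 5.6 = 8.7%, against 8.8% observed. The excess comes mainly from the zero-variance fits.

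**5. Interval.** At 25% v 50% and ICC 0.05, the nominal 95% Wald interval covered 91.5% (192) and 91.0% (227), with 5,000 replicates each.

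**6. Other references for the planned model, ICC 0.05.** A t with 4 or 5 df rejected 1.2–2.5% in the separately coded repeat; 5 df gave 2.3–3.0% in the main set. A t with 10 df gave 4.4–5.8%, but 2.4% at ICC 0.

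**7. Randomisation test.** The hat draw makes 6! = 720 site orders equally likely. A score-type statistic from the planned model, recomputed over all 720 orders, rejected 4.9–5.5% for ICC 0 to 0.10 and all three time codings. Its inverted interval covered 94.2–95.2%. A version on the risk-difference scale rejected 4.8–5.5%, and 5.1–5.4% when programmed again.

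**8. Power at 25% v 50%, ICC 0.05 (5,000 replicates).**

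| Method | N 192 | N 227 |
|---|---|---|
| Randomisation test | 66% | 71% |
| Wald, cut-off raised to hold 5% | 66% | 70% |
| t, 10 df | 64% | 70% |
| Wald, uncorrected | 73% | 78% |

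At 192, power of the randomisation test is 74% at ICC 0.01 and 56% at ICC 0.10. The coverage, power and score-type randomisation results come from a single set of simulations.

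**The case against.** The best reply is that the plan commits to nothing. Section 3.8 names a model, not a test, so the inflation is an omission plus a hypothetical; a conservative t reference is equally compatible with the text. That stands. A reader might infer that the planned primary test is anti-conservative as written. The documents do not support that, because the size of the unnamed test could fall on either side of 5%.

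The excess is also modest, depends on the true ICC, and vanishes if sites do not differ. That stands too, but 0.05 is the only ICC that section 3.9 plans on.

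A further objection is that the randomisation test has its own condition. Re-ordering sites treats the enrolled participants as fixed. Yet eligibility is assessed in the last two weeks of the programme (section 3.4), and an exclusion for attending fewer than 4 of 6 discussion sessions applies to PROPEL only. The enrolled set could therefore depend on allocation. This is correct and must be stated, although the model-based test has the same weakness.

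Finally, a reader might take the power figures to mean that this point calls for more participants. It does not. The uncorrected Wald test also falls short of 80%, so the shortfall is a separate sample-size matter.

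**Conclusion.** The point holds as a conditional one. The plan is silent on inference for the phase effect with 6 sites. Running the stated model with its usual z or chi-square output would overshoot the stated alpha by about 2–4 points at the planning ICC and leave interval coverage near 91%. Defaulting to a t with 4 or 5 df would err the other way.

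The figures assume calendar time in the model, even recruitment over the 15 groups, a normal site intercept, no true time trend, no site-by-period or site-by-treatment variation, and enrolment that does not depend on allocation. The omission itself needs no assumptions. It should be corrected, though it does not invalidate the design.

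**What to change.** Before the data are seen, add to section 3.8 one prespecified inference method for the primary phase effect that holds its level with 6 sites. Preferred wording, for adaptation:

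> The primary phase effect will be tested by a two-sided randomisation test over all 720 assignments of sites to the Figure 1 sequences. The 95% confidence interval will be obtained by inverting the same test. The test assumes that the set of enrolled participants does not depend on allocation; because enrolment takes place at the end of the intervention and one attendance exclusion applies to PROPEL only, this assumption will be discussed in the report.

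The acceptable alternative is the planned model with a t reference whose degrees of freedom are fixed in advance and justified by simulation on the Figure 1 schedule. The exact statistic, time coding and any working site SD are for the sponsor's statistician to choose and record.

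Restate the section 3.9 power under the chosen method. For the randomisation test simulated here it is about 66% at 192 evaluable and 71% at 227.

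The cost is analysis programming, a less favourable stated power and a wider interval. In 500 simulated trials per size, the median log odds ratio width was 1.93 against 1.69 for Wald at 192 (1.93/1.69 = 1.14), and 1.79 against 1.61 at 227 (1.79/1.61 = 1.11), so about 11–14% wider. Inverting the test on the odds-ratio scale also assumes one odds ratio across sites and is approximate for binary data. No new data and no increase in enrolment are part of this change.

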### 3.9. Sample size

We expect that approximately 25% of people who complete GAE and 50% of individuals who complete PROPEL will be classified as 'active'. A sample of 96 per phase will provide 80% power to detect a 25% to 50% difference at alpha of 0.05 for the 6 sites taking into account an intracluster correlation of 0.05. The sample size calculation was run using PASS Version 12 (Hintze, J, 2014, NCSS, LLC. Kaysville, Utah). We will aim to recruit 120 participants total per phase to account for a conservative 20% drop-out rate; note that in our previous studies where participants were recruited at discharge from rehabilitation and followed for up to 6 months, the rate of withdrawal was much lower (<12%). There are 710 admissions annually to out-patient stroke rehabilitation at all sites combined. We conservatively estimate that approximately 40% of these individuals will be eligible for the study and, of these, 50% will consent to participate. Thus, we expect to recruit ~140 participants annually to meet the target sample size with ~2 years of recruiting (see timelines and milestones: Figure 3). Target sample sizes for each site are: St John's – 60, West Park – 60, Toronto Rehabilitation Institute (both sites) – 116, St Joseph's Care Group – 24, Hamilton Health Sciences – 24.

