### 3.7. Intervention allocation

The time at which each site transitions from GAE to PROPEL will be determined by drawing site names at random (see Figure 1 for full details). One site will implement PROPEL at the start of the study period, whereas one site will never transition to PROPEL; this will help to ensure blinding of assessors (see next section). The site that does not transition to PROPEL during the study period will be offered training in PROPEL at the end of the study period. Intervention allocation will be performed at the start of the study period by the principal investigator, who will not be directly involved in recruiting or data collection.

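### The 80% power for 96 per phase fits a parallel cluster trial; the planned stepped wedge with a time effect has about 74-76%

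*Combined protocol and SAP*

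**What the plan says.** Section 3.9 (Sample size) assumes that 25% of GAE and 50% of PROPEL participants will be active, and states: "A sample of 96 per phase will provide 80% power to detect a 25% to 50% difference at alpha of 0.05". The claim is qualified as being "for the 6 sites taking into account an intracluster correlation of 0.05". It names PASS 12 and a general text on cluster trials, but not the PASS procedure or its settings. It mentions no steps, periods or time effect. It then allows for loss: "We will aim to recruit 120 participants total per phase to account for a conservative 20% drop-out rate". That makes 240 recruited and 192 evaluable.

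The design is set out elsewhere. Figure 1 (Section 3.1) has 6 sites and 15 periods, where "G1, G2 etc. are the 6-week long group aerobic exercise (GAE) or PROPEL groups". Four sites cross over at staggered times. Section 3.7 fixes the other two: "One site will implement PROPEL at the start of the study period, whereas one site will never transition to PROPEL". For the primary outcome, Section 3.8 specifies "mixed-model logistic regression, with fixed effects of time and phase and random effect of cluster (site"). It does not say whether time means group period, a linear trend or calendar year.

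Section 3.2 rejects a conventional cluster trial because it "would not be ideal due to the relatively low number of sites (6), and thus, reduced statistical power".

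**The concern.** In a stepped wedge the share of sites on PROPEL rises over calendar time, so time and phase are correlated. Adjusting for time costs precision, while comparing phases within the same site gains it. A valid power figure has to reflect both, and Section 3.9 shows sign of neither. Section 3.2 also prefers the stepped wedge partly on grounds of power with 6 sites, so the power should be worked out for that design.

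At stake is how a null result would be read. Readers would set it against 80% power at 96 per phase. If the planned analysis does not deliver that, the chance of missing a true 25% versus 50% difference is higher than they are told.

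**Working it through.** **Inputs.** From Section 3.9: proportions 0.25 and 0.50, 96 per phase, alpha 0.05, ICC 0.05, 20% loss. From Figure 1: sites start PROPEL at G1, G4, G7, G10, G13 and never, giving 45 GAE and 45 PROPEL site-periods. From Section 3.8: fixed time and phase, random site. Assumed: a two-sided test (sidedness is not stated) and a mean outcome variance of (0.1875 + 0.25)/2 = 0.21875.

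**Step 1: reproduce the stated figure.** For a parallel two-arm design with 6 clusters of 16 in each arm:
- Unadjusted n per arm = (1.96 + 0.8416)² × (0.1875 + 0.25)/0.25² = 54.94.
- Design effect = 1 + (16 − 1) × 0.05 = 1.75.
- n per arm = 54.94 × 1.75 = 96.1.
- Power at 96 per arm: effective n = 96/1.75 = 54.86, SE = √(0.4375/54.86) = 0.0893, Φ(0.25/0.0893 − 1.96) = 79.9%.

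This matches, but it implies 12 clusters and no time effect. Splitting the 6 actual sites 3 versus 3, with 32 each, gives a design effect of 2.55 and power of 64.0%.

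**Step 2: power for the planned design.** I used generalised least squares on the site-by-period means:
- Between-site variance is 0.05 × 0.21875 = 0.01094; within-site variance is 0.95 × 0.21875 = 0.20781.
- Each cell holds (site total)/15 participants.
- The site effect is constant over time.
- Power = Φ(0.25/SE − 1.96).

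Results are given for equal sites and for sites in proportion to 60/64/52/60/24/24, averaged over all 720 orders of drawing. Section 3.9 gives 116 for the two Toronto sites together; I split it 64/52 in proportion to their 160 and 130 admissions.

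| Time coding, 192 evaluable | SE, equal sites | Power, equal sites | Power, unequal sites | Evaluable N for 80% |
|---|---|---|---|---|
| Categorical | 0.0945 | 75.4% | 74.0% | 223-232 |
| Linear | 0.0937 | 76.0% | 75.2% | 218-224 |
| Calendar year (two levels) | 0.0890 | 80.2% | 79.4% | 191-196 |
| Omitted | 0.0782 | 89.2% | 88.6% | – |

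With the unequal sizes, the most favourable order gives 74.4% (categorical) and 75.6% (linear), so no draw of sites reaches 80% under either coding.

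**Step 3: sensitivity to the ICC.** With categorical time and 192 evaluable, power is 80.8-82.2% at ICC 0.02, 77.9-79.3% at 0.03 and 69.7-70.9% at 0.10.

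**Step 4: check against the logistic model.** A random-intercept logistic model was simulated with equal sites, 1000 runs per setting and site-intercept variance 0.173 or 0.22 on the logit scale. Power was about 68-73% with five time blocks, 72-76% with linear time and 75-76% with calendar year. Rejection under the null was 6-9%. The approximation in Step 2 therefore does not exaggerate the shortfall.

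**Step 5: which total the power belongs to.** Section 3.9 aims for 2 × 120 = 240, but its site targets sum to 60 + 60 + 116 + 24 + 24 = 284. Each site target equals that site's two-year forecast. For example, 150 admissions × 0.4 × 0.5 × 2 = 60, and overall 710 × 0.4 × 0.5 × 2 = 284.

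| Recruited, loss | Evaluable | Power, categorical to linear time |
|---|---|---|
| 240, 20% | 192 | 74-76% |
| 240, 12% | 211 | 77-79% |
| 284, 20% | 227 | 79-81% |
| 284, 12% | 250 | 82-84% |

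**The case against.** The strongest points on the other side are these.

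- **The layout is inferred.** The PASS settings are not given. The parallel layout was the only variant tried that returned both 96 and 80%. This stands as a caveat on where the figure came from. Step 2 does not depend on it, because the planned design can be evaluated directly.
- **The gap depends on the time coding.** Under calendar-year coding the approximation gives 79.4-80.2%, so the stated 80% would survive. This is fair, but the plan does not commit to that coding, and the logistic simulation gave only 75-76% for it. A pooled outcome variance (0.2344) gives about 77%.
- **The gap is small.** It lies inside the spread produced by varying the ICC from 0.02 to 0.10. This is true and limits the severity, but Section 3.9 commits to 0.05 and the 80% is stated for that value.
- **Recruitment may absorb it.** At 284 recruited, power returns to about 80%, and Section 3.9 cites withdrawal below 12% in earlier studies. This also stands, but only if recruitment runs past the stated aim of 240. With 240 recruited, power is 74-79% depending on loss.
- **96 per phase is not held exactly.** With unequal sites, PROPEL receives about 75 to 117 of the 192, depending on the draw. The effect is minor: 73.4-74.4% across orders with categorical time.
- **The replacement figures are approximate.** They come from a linear model with the ICC on the proportion scale, whereas the planned model is logistic. This argues for a proper recalculation, and the checks made point to lower power, not higher.

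**Conclusion.** The concern holds. The sum behind the 80% is sound for a parallel cluster trial but does not fit this one. At 192 evaluable and ICC 0.05, the Figure 1 schedule with the Section 3.8 model has about 74-76% power with categorical or linear time. That is 4-6 points below the figure stated. It reaches about 79-80% only with time coded as calendar year, and only under the normal approximation.

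These figures rest on a two-sided z-test, outcome variance 0.21875, a site effect that does not vary over time, and even accrual within sites. With 6 clusters, a normal approximation is more likely to flatter than to understate power; I put no specific lower figure on it. The defect should be fixed but does not threaten the trial, since recruitment near the forecast of 284 would largely restore 80%.

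**What to change.** 1. In Section 3.8, state how time is coded in the primary model.
2. In Section 3.9, replace the calculation with one for the Figure 1 schedule and the Section 3.8 model, using the same time coding. State the sidedness, the outcome variance and the site sizes assumed.
3. Restate power at 192 evaluable and ICC 0.05. The recalculation should come out near 74-76% for categorical or linear time, or 79-80% for calendar year if a normal approximation is used. Add that such figures are likely optimistic with 6 clusters.
4. Label 240 as the required number and 284 as the accrual forecast, since the word target now covers both. Give the power for each after loss, as in the second table above.
5. Optionally, note that 15 February 2017 to the end of 2018 (the start day is assumed; Section 3.10 says mid-February) is 684 days, about 22.5 months. The forecast then becomes 142 × 684/365.25 = 266 recruited, or 213 evaluable after 20% loss, with about 77-79% power. This does not contradict the plan, which gives its rates and duration as approximate.

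The cost is new wording in two sections, one analysis decision (the time coding), and a stated power about 4-6 points less favourable at 192 evaluable unless calendar-year coding is chosen. The schedule, interventions, recruitment and data collection stay as they are.
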